Pending available funding, iron status will be assessed by serum iron and iron-binding capacity and serum ferritin concentrations. The importance of anemia and iron status has been demonstrated in both CKD progression and CVD.

3.E.5.n. Other Biochemical Measures

Electrolytes (Sodium, Potassium, Chloride, Bicarbonate), BUN, Creatinine, Glucose, AST, ALT, Total Bilirubin, Total Protein, Calcium, and CBC will be measured annually. A urine dipstick will be recorded annually for qualitative glucose, protein, and hematuria determinations. Magnesium, Phosphorous, Uric acid, and iPTH will be measured beyond baseline pending available funding.

3.E.5.o. Genotyping

Each patient enrolled in the NEPTUNE will be offered the opportunity to undergo mutational analysis by exon sequencing performed by The University of Michigan Genetics Laboratory. Mutation analysis will be obtained for the following Nephrotic Syndrome genes with recessive inheritance pattern: *NPHS1*, *NPHS2*, *LAMB2*, *PLCE1/NPHS3* and for the Nephrotic Syndrome genes with dominant inheritance pattern: *WT1* (and if indicated by family history also the extremely rare causative genes *TRPC6*, *ACTN4* and *CD2AP*). If no mutations are detected in these genes, the patient's DNA will be examined by exon capture and exon sequencing to detect mutations in so far unknown nephrosis-causing genes. If sibling cases with Nephrotic Syndrome become available in the study, they will be examined by homozygosity mapping with consecutive exon capture and exon sequencing. Genes postulated to infer risk of progression of glomerular disease (including *MYH9*) will also be considered.

3.E.5.p. Cell Line Growth and Immortalization

Pending available funding, cell immortalization of blood sample leukocytes will be pursued. Immortalized leukocytes may provide the raw material to understand the cellular and molecular mechanism of kidney disease pathways.

Schedule of Biologic Specimen Collection: Biologic specimens collected during the course of the cohort studies include blood, 24-hour urine, random spot urine, nail clippings, and renal biopsy tissue. The schedule of these collections is shown in Table 6.

Table 6. Schedule of Biologic Specimen Collection in Cohort Studies

Measure	Collection Schedule
Blood specimen	Every visit
Renal biopsy tissue	Biopsy Visit and as clinically indicated
24-hour urine specimen	Every visit
Spot urine specimen	Every visit

3.E.6. Other Exploratory Exposure and Intermediate Outcome Variables**3.E.6.a. Sociodemographic and Medical History**

Data on age, gender, detailed race/ethnicity, education and income will be collected at study baseline. Patient residential census tract will be collected at baseline. A directed history will be obtained to determine associated factors, family history of renal and cardiovascular disease, prior cardiovascular disease and risk factors, coexisting morbidity, and health behaviors (see Manual of Procedures).

3.E.6.b. Medications and Vaccination Use

Participants are asked to list all prescription and over-the-counter medications they have taken since last study visit, and any vaccines they have received since their last study visit. (see Manual of Procedures).

3.E.6.c. Quality of Life

A Quality of Life (QOL) assessment is being performed using the PROMIS questionnaire. It will be completed by all age participants (Parent report for ages < 10 years and self report for all others 8+ years of age) (see Manual of Procedures).

3.E.6.d. Health Care Resource Utilization

Health care resource utilization data are being collected using administrative claims data (e.g. in the subset of Medicare-eligible patients) and data obtained directly from cohort participants

at the follow-up visits. If funding becomes available, this resource will be comprehensively developed by our study team.

3.E.6.e. Medication Adherence Measure

Patient self – report for age 8 years and greater and parent proxy for age 0 to 10 years will contain questions on adherence to medicine regimens prescribed for kidney disease and reasons for missing medications.

3.E.6.f. Occupational Exposures to Heavy Metals

Pending additional funding, exposure risks to heavy metals will be assessed in both cohorts in a structured questionnaire currently being developed by the NEPTUNE under the leadership of the University of North Carolina.

3.E.6.g. Pregnancy History

Pending additional funding, a detailed pregnancy history including pregnancy outcomes will be assessed in both cohorts in the NEPTUNE study by direct participant questioning as well as chart review as needed.

3.F. Statistical Analysis

3.F.1. General Methods for Statistical Analysis

We plan to use standard descriptive statistics to characterize the overall study population and subgroups of interest both at baseline and during follow-up. Summary statistics such as means, medians, standard deviations, and ranges will be produced for measured variables. Frequencies will be tabulated for categorical and ordinal variables. Graphical methods will be used extensively to examine distributions, identify potential influential points, and guide in data transformations if warranted. For outcomes collected longitudinally, and to examine associations among various measures, scatterplots and grouped boxplots will be produced to examine assumptions of linearity, symmetry, and homoscedasticity. We can also easily calculate the rate and adjusted hazard rate of the main two clinical outcomes (change in UPE and renal function) using regression methods.

3.F.2. Analysis During the Adaptive Recruitment Phase

The study has several recruitment goals regarding the distribution of various groups, including the distribution of serum creatinine or eGFR, age and other characteristics. At some clinical centers, these measures will be available in advance from automated electronic databases; at others, the data will be available only at the time of the initial clinic visit.

In the sections above, we specified recruitment targets by histological diagnosis. During the course of recruitment, we will examine repeatedly these characteristics by center using the web-based, real-time monitoring function of NEPTUNELink. If, after completion of the recruitment of 300 participants, the distributions of these variables are close to the target ranges specified above, recruitment will be continued as previously described. If not, participants with some levels of these variables were oversampled and others undersampled and corrective measures will be taken to ensure adequate representation of both cohorts. Related statistical analysis will account for this unbalanced sampling through appropriate weighting schemes.

During the protocol revision for Version 3.0, the DACC regarded the number of diagnoses entered into the OG Cohort (Other Glomerulopathies) to be higher than anticipated. In an effort to maintain statistical power for the cohorts of interest (FSGS/MCD and MN) for the study's goals, the overall recruitment target goal was adjusted to 600 to reach the projected targets of 250 and 200 for the FSGS/MCD and MN cohorts, respectively.

Other measures, including screen failure for consented individuals determined to have exclusion criteria present post-enrollment, have been taken to compensate for over-enrolling in the OG group. The OG group will not be further followed, but samples and data obtained will remain available for comparative analyses.

3.F.3. Special Considerations for the Analysis of Molecular Biomarkers

[figure not shown]
The analysis of molecular biomarkers aims to identify promising genetic signatures used in the building of a prediction model for clinical outcomes. To screen the large number of potential predictors without losing analytical power, we would proceed in a hypothesis generating manner. Regression analysis of the clinical endpoint on biomarkers allows us to obtain P-values in the testing of their association, and a threshold value of false discovery rate would be set to determine a pool of potentially important biomarkers. These selected biomarkers will then be analyzed and grouped according to the relevance of their biological functions available in various databases. For example, biomarkers in a common transcriptional network may form a molecular signature panel. Such various panels can be further tested for the association with the clinical endpoint via the method of ridge regression. Ridge regression enables us to bypass the analytic difficulty due to highly correlated biomarkers in the model and hence obtain robust results.

3.F.4. Prediction Model Combining Molecular Biomarkers and Auxiliary Variables

The primary objective of the data analysis is to build a predictive model that uses both molecular biomarkers and auxiliary predictors to classify patients into one of two clinical states of the primary endpoint, Complete Remission/Partial Remission (CR/PR) and No Remission/Relapse (NR/R). The second endpoint is the presence or absence of the loss of renal function. In addition to 20,000 molecular markers, there are 74 auxiliary predictors collected from both cohort studies, including 38 histopathology variables, 15 laboratory variables, 15 clinical and demographic information variables, and 6 treatment variables.

Given the large number of predictors, we take a three-stage data analysis strategy consisting of variable screening, model building, and model validation. Figure 1 shows a schematic flow of steps for the model building.

Figure 1: Schematic illustration of analytic steps taken to model building.

The first stage of analysis is a variable screening analysis, in which we perform univariate analysis. The aim of this study is to evaluate basic distributional characteristics of each predictor and pairwise correlation between the response and each predictor, as well as that between each pair of predictors. In this analysis, we also examine if transformations on some predictors are needed and if high-order predictors such as interactions and polynomial predictors are potentially useful predictors.

At the second stage of analysis, we build a predictive model for the clinical endpoint. First, we perform univariate logistic regression of the clinical endpoint on each of the predictors to detect promising predictors. To deal with the multiplicity in the test, we control a common significance level α_m on molecular markers and α_c on auxiliary predictors. At different levels of α_m and α_c , we obtain several sets of molecular and auxiliary predictors. For example, we may control α_m at 10^{-8} and α_c at 10^{-4} according to the Bonferroni's conservative type I error control. Using a set of the selected predictors, we invoke ridge logistic regression to build a predictive model, which essentially provides a linear classifier to determine the membership of a patient with a clinical class.

At the final stage of model building, we use the ROC curve method to select the final model from a small pool of candidate predictive models. To do this, we split the sample into the training set and the test

set at $(2/3n):(1/3n)$ (96-98) randomly with multiple rounds, say 100. For the sample size 200, the split is 135:65, and for the sample size of 250, the split is 170:80. At each round, we use the training set to build a predictive model and the test set to evaluate its performance of prediction by the AUC, acronym for the area under the receiver operating characteristic (ROC) curve. We use the averaged AUC to determine the final predictor model with the best averaged prediction power.

3.F.5. Sample Size and Power Considerations

3.F.5.a. Overview

The primary aim of this study is to build up the prediction model, so our sample size and power calculation should be based on this goal. Following Dobbin and Simon (96), we adopt the expected probability of correct classification (PCC) as the measure of predictive power, which is approximately equal to the AUC, acronym for the area under the receiver operating characteristic (ROC) curve. This study focuses on two rare diseases: FSGS/MCD and MN, so we use PCC to evaluate the sample size of these two diseases, respectively.

3.F.5.b. Sample Size and Power Related to the FSGS/MCD Cohort Study

PCC is the probability of correct classification obtained on an infinite sample size and should be the gold standard of the best power. FSGS and MCD are rare diseases; it is unrealistic to find very large sample sizes to approximate the result under an infinite sample size. However, we will be able to find the PCC under realistic sample sizes, and we use PCC* to denote it. PCC* is the expected probability of correct classification with the optimal linear classifier constructed from the true molecular markers and auxiliary predictors. The results given in Table 6 are based on a simplified analysis with conservative assumptions. We screen 20,000 genes (probes) and 75 auxiliary predictors, in which there are r_m true gene expression markers and r_c true auxiliary predictors for the clinical endpoint. Ratio δ_m/σ_m is the average effect size of a single molecular marker, and the relative effect size of the auxiliary predictor to the molecular marker is 0.5. Also, ρ is the correlation between molecular markers and auxiliary predictors, and $\rho=0$ is assumed in Table 7 (3.N-2 below).

Table 7. Probability of Correct Classification

$r_m = 5, r_c = 10$				
δ_m/σ_m	PCC*	PCC(n=100)	PCC(n=150)	PCC(n=200)
0.2	0.788	0.638	0.667	0.687
0.4	0.941	0.876	0.892	0.896
$r_m = 50, r_c = 10$				
δ_m/σ_m	PCC*	PCC(n=100)	PCC(n=150)	PCC(n=200)
0.2	0.941	0.638	0.695	0.753
0.4	0.999	0.987	0.995	0.996
$r_m = 100, r_c = 10$				
δ_m/σ_m	PCC*	PCC(n=100)	PCC(n=150)	PCC(n=200)
0.2	0.982	0.672	0.766	0.837
0.4	0.99999	0.9994	0.99990	0.99994

For example, if we have 50 molecular markers and 10 auxiliary variables, from the sample size of 200, we will be able to reach a 99.6% PCC* with the average effect size of a single molecular marker to be 0.4, and the relative effect size of the auxiliary predictor to the molecular marker to be 0.5. This 99.6% PCC* almost reaches the optimum PCC of 99.9%, yet it is very realistic because the sample size of 200 falls in our recruitment targets.

It is noted that the inclusion of patients without the specified diseases of interest will not affect the power of classifier designed for this study as long as the required sample sizes given

in Table 7 are met. Such additional information from the third cohort might be useful in the development of a different classifier in an auxiliary study where the clinical status of these patients is of interest.

3.F.5.c. Sample Size and Power Related to the MN Cohort Study

Under the same assumption given in the power calculation for the FSGS/MCD cohort study, we can also calculate the power of the MN cohort study in the same fashion. And the result provided in Table 7 above (3.N-1) can also be applied to the MN cohort study.

For example, if we have 100 molecular markers and 10 auxiliary variables, from under the sample size of 150, the PCC* is 76.6% with δ_m/σ_m being 0.2 and the relative effect size of the auxiliary being 0.5. If we increase the sample size from 150 to 200, we can find an increase of PCC* from 76.6% to 83.7%.

3.F.5.d. Sample Size and Power Related to the cNEPTUNE Study

The analytic plan for this cohort is to identify groups of participants by clinical relapse and remission patterns as well as functional, molecular and genetic profiles, with a goal to relate those groups to clinically meaningful outcomes, including patient reported outcomes. As these subgroups are yet to be defined by the data obtained by the cohort, we present a range of exposures and minimum detectable odds ratios below. In the pediatric population, and as seen in the current NEPTUNE cohort, rates of clinically significant decline in kidney function, defined as a 40% drop in eGFR or ESRD, ranged from 0.00 to 0.16 per person-year, and as such, the study is not primarily powered to this event.

The statistical power calculations are based on the following assumptions. We conservatively assume a loss of 10% of the available follow-up due to participant retention issues. We assume a power of 80%, an alpha of 0.05, an intra-cluster correlation of 0.05, and a between-facility normalized standard deviation of the sample size of 0.15.

Power was computed for a range of sample sizes, event rates, and exposure percentages, representing between- and within-group comparisons and outcomes as described within each aim (Table H). For example, the 50% v. 50% exposure would correspond to an analysis across the entire sample between participants above v. below the median of a continuous covariate. Other percentages correspond to group comparisons of specific biomarker samples or among specific populations (e.g. participants with specified biomarkers, functionally defined subgroups). In each row, the minimum detectable odds ratio (MDOR) using logistics regression is provided with a varying outcome prevalence.

Exposure Percentages		Logistic analyses	
Group A	Group B	Outcome Prevalence	MDOR
50%	50%	35%-45%	2.3
		20%	2.7
20%	80%	35%-45%	2.8
		20%	3.1
20%	40%	35%-45%	3.1
		20%	3.6
10%	50%	35%-45%	6.4-6.9
		20%	6.7

3.F.5.e. Time to Event Analyses

Cox regression will be applied to analyze the time to event data of the primary or secondary endpoints collected in both cohort studies. This analysis allows us to assess association of the disease hazard rate with either clinical covariates of interest or genetic signature panels. Moreover, a survival distribution function of emission or that of renal function loss can be estimated under different patient profiles. A possible complication in the analysis is that patients may experience recurrences of remission, partial remission or no remission during the follow-up period. Thus, it is also of interest to perform an analysis of recurrent event history data, and to compare the results with those obtained from the only endpoint-based time to event analysis.

3.F.6. Data Management Infrastructure

The consortium data collection and management will be accomplished using Arbor Research ArborLink, regulatory-compliant, web-based clinical research information system. ArborLink is licensed and supported by the Arbor Research Collaborative for Health (Arbor Research); its use by NEPTUNE will be supported by Arbor Research. A NEPTUNE specific version of ArborLink will be henceforth called NEPTUNE-Link. Among its many attributes, this system allows systematic remote web-based clinical and laboratory data collection at study participant encounter sites, and provides patient tracking, and data management capability.

The SMS system will be managed using the NEPTUNE-Link data management system to supply information for message tailoring, Intervision, Inc. for routing of SMS messages to designated patient/parent recipient and return of messaging responses for storage to the NEPTUNE data storage at Arbor Research, Ann Arbor, MI.

As mandated by the funding agency, select data will be transferred to the central Data Management and Coordination Center (DMCC) of the RDCRN.

NIH Approved 03/29/2019

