Disease Status Home Monitoring: Collection of patient reported information (PRI) will be captured from the home environment using text messaging prompts. Automatic text messages will consist of daily messages sent for the first 3 months, and weekly for the subsequent 9 months. Information gathered will include home urine protein test results, nephrotic syndrome triggers (allergies, infection, stressors), edema status, consumption of prescribed immunosuppression, and nephrotic syndrome related absences from work/school. Alerts will be sent to the study team if the patient has $\geq 2+$ urine protein for 3 days after being negative/trace, new onset swelling in the abdomen, genitals, or anasarca or if the patient/parent fails to respond to text messages for a week. Either the patient (≥ 12 yrs) or parent may respond to the text messages at the discretion of the parent/child dyad with approval from the local study team and IRB.

Home Urine Protein Monitoring: Home urine protein testing using Chemstix™ will be performed daily for the first 90 days, weekly for the next 9 months (total 1 year) Results of this testing will be reported with SMS text messaging system and confirmed at study visits. Study participants will be supplied Chemstix™ as part of the cNEPTUNE cohort study.

3.B. Study Patient Population and Participant Distribution

Each of the Clinical Centers will enroll participants during the recruitment period. A recruit-to-replace enrollment strategy will be implemented during the entire enrollment period to ensure that the final sample size is preserved.

These diagnostic criteria are based on a uniformly accepted minimum requirement for clinical diagnosis of the respective conditions in North America. As standardized guidelines and findings from new studies become available, it is anticipated that the definitions for these glomerular disorders will evolve.

Participants initially enrolled in the NEPTUNE study whose post-enrollment renal biopsy histopathology does not fulfill the histopathologic criteria of FSGS/MCD or MN will no longer be followed in the study with the exception of cNEPTUNE where a child will continue to be followed in the cNEPTUNE cohort until the completion of the 12 month visit if the kidney biopsy is not consistent with the FSGS, MCD, or MN pathology criteria. cNEPTUNE participants with biopsy fulfilling the FSGS, MCD or MN pathology criteria will remain in long-term cNEPTUNE study observation as outlined in section 3.D.1.

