Participants enrolled in cNEPTUNE with subsequent clinically indicated kidney biopsy will participate fully in the biopsy component of the protocol. Consent will be obtained. The biopsy tissue will be collected, pathology report and slides will be reviewed for pathology classification of NS according to the criteria in 3.B.1 and 3.B.2. Children enrolled in cNEPTUNE with kidney biopsies that do not meet FSGS, MCD or MN criteria will be classified by pathology diagnosis and retained in the cNEPTUNE cohort to complete all protocol defined study visits and procedures. Entry Age Range is consistent with Cohort B eligibility.

There is no lower age limit for inclusion/exclusion in the NEPTUNE study for the FSGS/MCD and MN cohorts. Adults < 80 will be approached for inclusion. Participants must be < 19 years of age for consideration into cNEPTUNE.

3.B.4. Inclusion Criteria for Cohort A

Potential participants for the FSGS/MCD and MN Cohorts will be required to fulfill the following criteria:

- A new diagnosis of FSGS or MCD or MN according to characteristic light, electron (EM), and immunofluorescence microscopy (IM), with presence of at least five glomeruli per biopsy available for analysis. Biopsy slides will be reviewed and diagnosis confirmed by 2 study pathologists according to standardized criteria developed by the pathology committee (see Appendices C and D);
- Documented urinary protein excretion ≥ 1500 mg/24 hours or spot protein:creatinine ratio equivalent at the time of diagnosis or within 3 months of the screening/eligibility visit. Alternatively, an albuminuria equivalency determined by the local site PI;
- < 80 years of age
- Completion of V1 (baseline visit) within 45 days of V_{BX} (biopsy visit)
- Informed Consent

3.B.5. Inclusion criteria for Cohort B

Potential participants for Cohort B, cNEPTUNE will be required to fulfill the following criteria:

- <30 days of treatment for nephrotic syndrome
- Proteinuria/Nephrotic defined as:
 - Urinalysis with >2+ protein AND edema OR
 - Urinalysis with >2+ protein AND serum albumin < 3 OR
 - Urine protein:creatinine ratio >2 AND serum albumin <3
- Age <19 years
- Informed Consent and Assent when applicable

3.B.6. Exclusion Criteria for Cohort A

- Prior solid organ transplant
- A clinical diagnosis of FSGS/MCD or MN without diagnostic renal biopsy

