This information will be inputted into NEPTUNE-Link and will be automatically transferred to the SMS system. Participant responses to text messages will be returned to NEPTUNE-Link for the local study team to review.

Participants will receive text messages asking about home urine protein monitoring results, relapse triggers (infections, allergies, stressors), edema status and location, consumption of prescribed immunosuppressive medications and nephrotic syndrome related absences from school/work. Parent or child (≥ 12 yrs) can respond to text messages at the discretion of the parent/child dyad (with approval from coordinator/local PI). The SMS alert system may be paused for planned vacations or during hospitalizations by the site study coordinator. SMS pause start and end dates will be entered into the NEPTUNE-Link SMS administration CRF to implement the pause.

Alerts will be sent to the email addresses designated in NEPTUNE-Link for items such as dipstick $\leq 2+$ for 3 days after being trace/negative, abdominal or genital edema, anasarca, if the patient reports not taking immunosuppressive medications, or if there is no response for one week without prior notification to the study team to “pause” the system.

3.E. Study Data

Extensive data will be collected during the NEPTUNE cohort studies. These data descriptions are provided in the following six sections:

- 1) Primary Outcome Variables
- 2) Secondary Outcome Variables
- 3) Intra-renal Gene Expression Exposure Variables
- 4) Histopathology Variables
- 5) Overview Biochemical Measures
- 6) Other Exploratory Exposure and Intermediate Outcome Variables

3.E.1. Primary Outcome variables

The two primary outcome variables are:

- (1) Event rate of change in urinary proteinuria excretion (defined as remission, partial remission and non-remission); and
- (2) Rate of change in renal function defined as:
 - (a) 25 mls/min/1.73m² reduction in follow-up estimated GFR (using the 4-variable MDRD equation for ages ≥ 18 years and modified Schwartz for ages < 18 years) compared to baseline estimated GFR
 - (b) 50% decline in follow-up estimated GFR compared to baseline measurement
 - (c) End stage renal disease defined as estimated GFR ≤ 10 cc/min, initiation of maintenance dialysis or preemptive kidney transplantation).

3.E.1.a. Proteinuria

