Proteinuria (U:C) After Observation Period	Standard Definition	Definitions for the Cohorts
$U:C \leq 0.3g$	Complete Remission (CR)	Complete/Partial Remission
Reduction in U:C of $>50\%$ plus final $P:C \leq 3.5g$ but $>0.3g$	Partial Remission (PR)	
Reduction in U:C of $>50\%$ with final $P:C > 3.5g$	Limited Response (LR)	No Response
Reduction in U:C of $<50\%$. (include increase in U:C $<50\%$)	Non-Response (NR)	
Proteinuria increases by $>50\%$	Progressive Proteinuria (PP)	
New development of nephrotic range proteinuria, i.e., >3.5 P:C after reaching a complete or partial remission	Relapse	Relapse

3.E.1.b. Renal Function

The main renal function measures in the cohort studies include serum creatinine, serum Cystatin C, a 24-hour urinary clearance of creatinine, and estimated GFR using the MDRD equation for adults and modified Schwartz formula for continent children under 18 years. Serum Cystatin C assay will be deferred until funds for ancillary studies become available. The schedule of these measures is summarized in Table 4.

Table 4. Schedule of Renal Function Measurements in the NEPTUNE main cohorts

Measure	Collection Schedule
Serum creatinine	Every visit
24-hour urinary creatinine excretion	Every visit
Estimated GFR	Every visit
Serum Cystatin C	Every visit*

* Funds pending

3.E.1.b.(a) Creatinine-based Measures

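### The home-dipstick alert in 3.D.1.a.(b) SMS System is printed as 2+ or less, the reverse of the 2+ or more given for the same alert in 3.A.2

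*Protocol*

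**What the plan says.** The alert is described twice in the Protocol, both times for Cohort B (cNEPTUNE).

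- Section 3.A.2, Disease Status Home Monitoring: "Alerts will be sent to the study team if the patient has $\geq 2+$ urine protein for 3 days after being negative/trace".
- Section 3.D.1.a.(b) SMS System: "Alerts will be sent to the email addresses designated in NEPTUNE-Link for items such as dipstick $\leq 2+$ for 3 days after being trace/negative". The same sentence goes on to list abdominal or genital edema and anasarca, and then "if the patient reports not taking immunosuppressive medications, or if there is no response for one week" (the last of these only when no pause was arranged beforehand).

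The readings that feed the alert are set in 3.A.2, Home Urine Protein Monitoring: testing "will be performed daily for the first 90 days, weekly for the next 9 months (total 1 year").

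The direction in which a dipstick signals disease can be read from the Cohort B entry criteria in 3.B.5, where one route into the study is "Urinalysis with >2+ protein AND edema OR".

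**The concern.** The two sections agree on the cohort, the home test, the messaging system, the three-day duration and the starting state. They differ only in the direction of the inequality. A notification threshold that points two ways leaves a site or a programmer to choose between them. Section 3.D.1.a.(b) is a natural place to look, because it also sets out the message recipients, the routing of responses and the pause function.

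At stake is prompt notice to the site when a child with new-onset nephrotic syndrome goes from a clear dipstick back to heavy proteinuria. A system set to 2+ or less would stay silent on the heavier relapses.

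**Working it through.** The plan gives no figure to reproduce. The check has three parts: which section is reversed, what each rule does to a given run of readings, and when the rule can operate at all.

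**1. Which section is reversed**

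- *The qualifier.* Negative and trace are themselves below 2+. A rule of 2+ or less after negative or trace does not need any worsening, so the qualifier does no useful work. With 2+ or more, it marks a change from clear to proteinuric.
- *The companion items.* Edema, anasarca, missed immunosuppression and a week of silence are all warning signs. Low protein does not belong in that list.
- *Entry criteria (3.B.5).* A reading above 2+ is part of the nephrotic definition, so high means active disease.

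All three point to 2+ or more, as in 3.A.2.

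**2. What each rule does**

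Assumptions: one reading a day, a rolling three-day window, and at least one negative or trace reading before the window. The protocol does not list the dipstick scale. I take it as negative, trace, 1+, 2+, 3+, 4+; nothing below changes if it stops at 3+.

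| Readings | 3.A.2 rule (≥2+) | 3.D.1.a.(b) rule (≤2+) |
|---|---|---|
| Negative, then three days above 2+ | fires once, on day 4 | does not fire |
| Negative, then three days at exactly 2+ | fires once, on day 4 | fires once, on day 4 |
| Negative, then three days at 1+ | does not fire | fires |
| Negative or trace on all 90 daily tests | does not fire | 0 or 87 days, see below |

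The first row holds however the qualifier is read. The last row does not:

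- If a child who simply stays negative or trace counts as being at 2+ or less after negative or trace, the rule is met on every day from day 4 to day 90: 90 − 3 = 87 days.
- If the wording requires the child to have left the negative or trace state, it is met on 0 days.

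The text does not settle which reading applies, so the range is 0 to 87.

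**3. When the rule can operate**

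- Daily readings: 90.
- Weekly readings for the rest of the year: (365 − 90)/7 = 39.3, about 39.
- Total scheduled: about 129.
- Daily phase as a share of readings: 90/129.3 = 0.70.
- Daily phase as a share of the year: 90/365 = 0.25.

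Three consecutive daily readings exist only in the daily phase, so the conflict between the sections matters mainly in the first 90 days. These shares describe the testing schedule. They do not measure harm. The protocol gives no alert or relapse counts, so the number of children affected cannot be estimated.

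**4. Could the sign be a conversion error?**

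The text was machine-read from a PDF, and the disputed sign is a single mathematical symbol. Comparable symbols print in the sensible direction: the one in 3.A.2, the age limit of 12 years or more for text responders in 3.D.1.a.(b) itself, and Table 3, for example "Reduction in U:C of $>50\%$ plus final $P:C \leq 3.5g$ but $>0.3g". That makes a misread unlikely, but it does not verify this symbol.

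**The case against.** The strongest reply is that this is a typographical slip that corrects itself. Section 3.A.2 states the rule fully and correctly, and it is at least as binding as 3.D.1.a.(b). The list in 3.D.1.a.(b) is introduced as examples, and the company the item keeps tells any clinician what was meant. Section 6.B.3 leaves detailed instructions to the Manual of Procedures, which is not at hand, and neither is the programmed rule. All of this stands, and it keeps the point minor. It does not remove it: an illustrative list can still state a threshold wrongly, and a correct statement elsewhere is what makes the two sections inconsistent.

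The second reply concerns size. A reader might infer that the printed rule would flood sites with 87 alerts for each child in remission. The documents do not support that as a fixed figure. It depends on reading the qualifier without a change of state, and it describes a child already clear at the first test, although entry requires nephrotic-level findings and less than 30 days of treatment. Such a child is possible, but nothing shows the pattern to be typical. Only the missed move to above 2+ survives both readings.

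The third reply is that other safeguards remain. Section 3.D.1.a.(b) says "Participant responses to text messages will be returned to NEPTUNE-Link for the local study team to review", and 3.A.2 says "Results of this testing will be reported with SMS text messaging system and confirmed at study visits". The edema, adherence and non-response alerts are unaffected by the sign. This also stands.

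**Conclusion.** The inconsistency is real and minor. Section 3.D.1.a.(b) SMS System prints the dipstick alert in the opposite direction to 3.A.2, and the protocol's own content shows that 3.A.2 is right. Read literally, the reversed rule misses a relapse from negative or trace to above 2+. Its behaviour in sustained remission ranges from 0 to 87 alert days over 90 clear daily tests, depending on the reading of the qualifier.

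Three stronger conclusions might be inferred, and the documents support none of them:

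- *That the protocol rules out an alert above 2+.* It does not: 3.A.2 provides for that alert, and the 3.D.1.a.(b) list is illustrative.
- *That relapses went unnoticed.* This would require the alert to have been programmed from 3.D.1.a.(b), which nothing shows. If it was programmed as in 3.A.2, the number of children affected is zero.
- *That study results are at risk.* The remission definitions in Table 3 rest on the urine protein:creatinine ratio, and text responses return to NEPTUNE-Link for review. No endpoint, power figure or analysis uses the alert threshold.

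Confidence is medium, because a misread symbol in the PDF conversion is unlikely but cannot be excluded.

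**What to change.** In 3.D.1.a.(b) SMS System, change the threshold from ≤2+ to ≥2+ so that it matches 3.A.2. Confirm once that the rule programmed in NEPTUNE-Link and the SMS system is 2+ or more. Only if it was programmed in reverse, go back through the stored responses for runs of three days at or above 2+ after a negative or trace reading that raised no alert.

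The cost is one symbol and one configuration check. The visit schedule, data collection, sample size and analysis are unchanged.
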